5.3. Exclusion criteria for enrolment

Deviations from exclusion criteria are not allowed because they can potentially jeopardize the scientific integrity of the study, regulatory acceptability or subject safety. Therefore, adherence to the criteria as specified in the protocol is essential.

The following criteria should be checked at the time of study entry. If ANY exclusion criterion applies, the subject must not be included in the study:

- Current TB disease or *history of TB disease and/or treatment for TB (including IPT)*. (Amended: 29 January 2014)
- Use of any investigational or non-registered product (drug or vaccine) other than the study vaccines within 30 days preceding the first dose of study vaccine, or planned use during the study period.
- Planned administration/administration of a vaccine not foreseen by the study protocol in the period starting 30 days before and ending 30 days after each dose of vaccine.
- History of previous administration of experimental Mtb vaccines.
- Chronic administration (defined as more than 14 days in total) of immunosuppressants or other immune-modifying drugs within six months prior to the first vaccine dose. (For corticosteroids, this will mean prednisone ≥ 20 mg/day or equivalent.). Inhaled and topical steroids are allowed.
- Any condition or illness (acute, chronic or history) or medication, which in the opinion of the Investigator might interfere with the evaluation of the safety or immunogenicity of the vaccine.
- Any confirmed or suspected immunosuppressive or immunodeficient condition, based on medical history and physical examination (no laboratory testing required).
- Planned participation or participation in another experimental protocol during the study.
- Concurrently participating in another clinical study, at any time during the study period, in which the subject has been or will be exposed to an investigational or a non-investigational product (pharmaceutical product or device).
- Administration of immunoglobulins and/or any blood products within the 3 months preceding the first dose of study vaccine or planned administration during the study period.
- History of any reaction or hypersensitivity likely to be exacerbated by any component of the vaccines.
- History of medically confirmed autoimmune disease (*e.g. Type I diabetes, Lupus*). (Amended: 29 January 2014)
- Pregnant or lactating female.
- Female planning to become pregnant or planning to discontinue contraceptive precautions during the vaccination period and/or before 2 months after completion of the vaccination series.

6. CONDUCT OF THE STUDY

6.1. Regulatory and ethical considerations, including the informed consent process

The study will be conducted in accordance with all applicable regulatory requirements.

The study will be conducted in accordance with the ICH Guideline for Good Clinical Practice (GCP), all applicable subject privacy requirements and the guiding principles of the Declaration of Helsinki.

GSK will obtain favourable opinion/approval to conduct the study from the appropriate regulatory agency, in accordance with applicable regulatory requirements, prior to a site initiating the study in that country.

Conduct of the study includes, but is not limited to, the following:

- Institutional Review Board (IRB)/Independent Ethics Committee (IEC) review and favourable opinion/approval of study protocol and any subsequent amendments.
- Subject informed consent.
- Investigator reporting requirements as stated in the protocol.

GSK will provide full details of the above procedures to the investigator, either verbally, in writing, or both.

Freely given and written (or thumb printed and witnessed) informed consent must be obtained from each subject, as appropriate, prior to participation in the study.

GSK Biologicals will prepare a model Informed Consent Form (ICF) which will embody the ICH GCP and GSK Biologicals required elements. While it is strongly recommended that this model ICF is to be followed as closely as possible, the informed consent requirements given in this document are not intended to pre-empt any local regulations which require additional information to be disclosed for informed consent to be legally effective. Clinical judgement, local regulations and requirements should guide the final structure and content of the local version of the ICF.

The investigator has the final responsibility for the final presentation of the ICF, respecting the mandatory requirements of local regulations. The ICF generated by the investigator with the assistance of the sponsor's representative must be acceptable to GSK Biologicals and be approved (along with the protocol, and any other necessary documentation) by the IRB/IEC.

6.2. Subject identification and randomisation of treatment

6.2.1. Subject identification

Subject identification numbers will be assigned sequentially to the subjects who have consented to participate in the study, according to the range of subject identification numbers allocated to each study centre.

6.2.2. Randomisation of treatment

6.2.2.1. Randomisation of supplies

The randomisation of supplies within blocks will be performed at GSK Biologicals, using MATERial EXcellence (MATEX), a program developed for use in Statistical Analysis System (SAS[®]) (Cary, NC, USA) by GSK Biologicals. Entire blocks will be shipped to the study centres /warehouse(s).

To allow “The Collaboration” to take advantage of greater rates of recruitment than anticipated at individual centres in this multi-centre study and to thus reduce the overall study recruitment period, an over-randomisation of supplies will be prepared.

6.2.2.2. Treatment allocation to the subject

6.2.2.2.1. Study group and treatment number allocation

The target will be to enrol approximately **3506** eligible subjects who will be randomly assigned to two study groups in a 1:1 ratio (approximately **1753** subjects in each group). **(Amended: 29 January 2014)**

Allocation of the subject to a study group at the investigator site will be performed using **an internet based** randomisation system (SBIR). The randomisation algorithm will use a minimisation procedure accounting for:

- **Centre (Amended: 29 January 2014)**
- Gender: a maximum of **2100** females/males will be recruited. **(Amended: 29 January 2014)**

Minimisation factors will have equal weight in the minimisation algorithm.

The treatment numbers will be allocated by dose at the site of the investigator using SBIR.

After obtaining the **informed consent** from the subject and having checked the eligibility of the subject, the site staff in charge of the vaccine administration will access SBIR. Upon providing the subject identification number, the randomisation system will determine the study group and will provide the treatment number to be used for the first dose. The number of each administered treatment must be recorded in the eCRF on the Vaccine Administration screen. **(Amended: 29 January 2014)**

When SBIR is not available, please refer to the SBIR user guide or the Study Procedures Manual (SPM) for specific instructions.

6.2.2.2.2. Treatment number allocation for subsequent doses

For each dose subsequent to the first dose, the study staff in charge of the vaccine administration will access SBIR, provide the subject identification number, and the system will provide a treatment number consistent with the allocated study group.

The number of each administered treatment must be recorded in the eCRF on the Vaccine Administration screen.

6.2.3. Allocation of subjects to assay subsets

Approximately **450** subjects will be included in the safety and immune sub-cohort. These subjects will be enrolled at selected centres. Blood sampling and safety assessment will be performed as described in [Table 4. Distribution of subjects in the sub-cohort is presented in Table 5.](#) (Amended: 29 January 2014)

Table 5 Distribution of subjects in the sub-cohort

Sub-cohort	Treatment group	N to be enrolled
Safety and immune sub-cohort	M72AS01	Approximately 225
	Control	Approximately 225

6.3. Method of blinding

The study will be conducted using double-blind procedures. The vaccine recipient, investigator and any person involved in the clinical conduct of the study will be unaware of which vaccine was administered.

The laboratory in charge of the laboratory testing will be blinded to the treatment, and codes will be used to link the subject and study (without any link to the treatment attributed to the subject) to each sample.

6.4. General study aspects

Supplementary study conduct information not mandated to be present in this protocol is provided in the accompanying SPM. The SPM provides the investigator and the site personnel with administrative and detailed technical *and operational* information that does not impact the safety of the subjects. (Amended: 29 January 2014)

6.4.1. Surveillance for safety and efficacy

Surveillance for efficacy starts with administration of the first dose of study vaccine or placebo.

6.4.1.1. Active follow-up for safety and efficacy

Subject safety follow-up and timely case capture of incident TB disease is of paramount importance. In addition to study visits at the study facilities, regular contacts (every two

months) with the study subjects must be maintained using one or more of the following methods:

- Regular interval home visits by site staff.
- Phone calls to inquire about current health status, completed by home visits if the subject cannot be reached.
- ***1-way short message service (sms) reminders and/or 2-way sms exchange.***

(Amended: 29 January 2014)

These active follow-up procedures for surveillance of safety and efficacy will be described in local study Standard Operating Procedures and ICFs. ICFs will be submitted to the Ethics Committee for approval prior to implementation.

During study visits and contacts, subjects will be asked if they have signs or symptoms of pulmonary TB. Based on clinical suspicion of TB, and guided by the World Health Organisation (WHO) signs and symptoms algorithm [WHO, 2009], they will be required to provide three sputum samples, preferably taken in the morning and within one week, to be tested for Mtb by Xpert MTB/RIF and microbiological culture.

6.4.1.2. Passive follow-up for efficacy

Subjects will be informed about signs and symptoms compatible with TB at the time of Informed Consent and at each visit/contact. At any time during the study, if a subject suspects that he/she has signs and symptoms of TB, he/she will be required to self-report to the study centre for clinical evaluation (passive follow-up) and if needed confirmatory testing using Xpert MTB/RIF and microbiological culture will be done.

6.4.2. Diagnostic procedures for the detection of suspected pulmonary TB

During the entire study period, when a subject presents with clinical suspicion of pulmonary TB, three respiratory sputum samples, preferably taken in the morning, must be collected, within a one week interval, for testing with Xpert MTB/RIF and microbiological culture. If results are negative but clinical suspicion of TB disease persists, the subject will be cared for according to local clinical practice (e.g. treated with non anti-tuberculosis antibiotics) and will be followed up approximately two weeks later. If clinical suspicion persists, three additional sputum samples, preferably taken in the morning, within a one week interval, will be collected for Xpert MTB/RIF testing and microbiological culture. If TB disease cannot be confirmed with Xpert MTB/RIF and/or microbiological culture, the subject may be given TB treatment based on other diagnostic tests (e.g. smear microscopy) and the judgement of the physician providing care.

Weight of the subject must also be recorded in the subjects' eCRF at the time of TB diagnosis.

Protocol samples for diagnostic testing with Xpert MTB/Rif and/or microbiological culture should preferably be taken before initiation of TB treatment. However, samples for diagnostic testing with Xpert MTB/Rif and/or microbiological culture may be

collected up to four weeks after initiation of TB treatment. Definite Pulmonary TB cases identified from sputum samples taken after initiation of TB treatment will not be included in the primary endpoint.

Testing results per protocol procedures will be communicated expeditiously to the investigator but their availability should not delay any diagnostic or therapeutic intervention as per local routine practice.

Additionally if TB is confirmed a serological test (and pre-test counselling) for HIV-infection must be performed to rule out HIV co-infection. If the subject is HIV-positive, additional testing must be performed to measure CD4 cell counts. ***Diabetes will be screened for by a Hb A1c test. (Amended: 29 January 2014)***

Results of HIV testing, including CD4 cell counts if applicable must be recorded in the subjects' eCRF. **(Amended: 29 January 2014)**

6.4.3. Diagnostic procedures for suspected extra-pulmonary TB

During the entire study period, when a subject presents with clinical suspicion of extra-pulmonary TB, a diagnostic procedure must be performed according to local clinical practice and as a minimum, the most recent WHO recommendations in the "International Standards for TB care" should be followed [[WHO](#), 2006].

The diagnostic procedures performed and their results must be recorded in the subjects' eCRF along with the final diagnosis of the attending physician.

Additionally, if extra-pulmonary TB is confirmed, a serological test (and pre-test **& post-test** counselling) for HIV-infection must be performed to rule out HIV co-infection must be taken. If the subject is HIV-positive, additional testing must be performed to measure CD4 cell counts. ***Diabetes will be screened for by a Hb A1c test. (Amended: 29 January 2014)***

Results of HIV testing, including CD4 cell counts, if applicable must be recorded in the subjects' eCRF. **(Amended: 29 January 2014)**

6.4.4. Procedures for fatalities

In order to diagnose the cause of death of fatalities occurring during this study, it is recommended that a verbal autopsy (VA) will be performed by the study staff for all fatalities, using a standardised VA questionnaire and cause of death qualification [[WHO](#), 2007].

Verbal Autopsy reports that are shared with ***the collaboration or any vendors acting on behalf of the collaboration must*** be anonymised, i.e. all personally identifiable information should be removed. ***In the event that this occurs a GSK data privacy breach form will need to be completed. (Amended: 29 January 2014)***

6.4.5. Safety Monitoring Plan

6.4.5.1. Safety Review Team

The Safety Review Team (SRT) includes as core members the GSK Biologicals' Central Safety Physician, the Clinical Development Manager, Epidemiologist, Clinical Regulatory Affairs representative and the Biostatistician of the project. The SRT will be responsible for ongoing safety monitoring of the study and will meet on a regular basis. In order to keep all people involved in the conduct, cleaning and final analysis of the study blinded, the SRT will monitor safety in a blinded manner.

6.4.5.2. Independent Data Monitoring Committee

In order to ensure the safety of the subjects during the entire study period, an Independent Data Monitoring Committee (IDMC) **has been** appointed to monitor the safety and tolerability of the vaccine/placebo administered in the trial and, if necessary, make recommendations to the sponsor concerning the modification or termination of the trial. The IDMC will perform safety reviews twice a year or more frequently if deemed necessary on an ongoing basis during the study period. **(Amended: 29 January 2014)**

An independent statistical team (i.e., comprising members who are neither GSK employees neither Aeras employees and who are not involved in the study management) will be appointed by GSK Biologicals. This team will be unblinded to treatment assignment and provide all necessary tables, listings, figures and individual subject data to the IDMC.

The IDMC consists of clinical experts who are not involved in the conduct of the study and an independent statistician. The role of the IDMC will be to review the progress of the trial and safety assessments to detect evidence of safety issues for the subjects from the time of first vaccination and throughout the duration of the trial. A report, with recommendations as necessary, will be provided to the sponsor following each IDMC meeting. The frequency of IDMC sessions and other operational details are described in the IDMC charter. In case of a serious safety issue during the study, the sponsor will inform the IDMC as well as fulfil its regulatory obligation expeditiously. **(Amended: 29 January 2014)**

If during the course of enrolment and vaccination two or more related grade 2 or 3 respiratory AE are observed an ad hoc IDMC will be convened. (Amended: 29 January 2014)

6.4.5.3. Planned safety review (Amended: 29 January 2014)

A planned safety review after the first 100 subjects have been enrolled and vaccinated will be performed. The SRT will review blinded safety summaries and the IDMC will review unblinded safety summaries.

6.4.5.4. Rules for vaccination (Amended: 29 January 2014)**At individual subject level**

- *No second dose should be administered in a given subject who experiences Grade 3 redness and swelling, i.e. $\geq 100\text{mm}$, post dose 1 or Grade 2 or 3 respiratory AE post dose 1.*
- *No second dose should be administered in a given subject who develops TB disease after dose 1.*

At study level

- *An ad hoc IDMC review will be called if 2 or more subjects experience related Grade 2 or higher respiratory AEs within 90 days after any dose.*
- *Further enrolment and vaccination will be suspended if within 90 days after any study vaccine dose any of the following events are observed:*
 - *Related respiratory AE with Fatal outcome*
 - *Two or more subjects experiencing Grade 3 related Respiratory AE*
- *An ad hoc IDMC meeting will be called urgently for review. Vaccination may only be allowed to resume pending final VSMB approval.*

Table 6 Safety holding rules for vaccination (Amended: 29 January 2014)

Event	Grade	Occurrences	Action for subject(s)	Trial actions
Redness/Swelling at injection site (within 30 days after dose 1)	Grade 3 (>100mm)	any subject(s)	No dose 2 in same subject(s), keep in efficacy follow-up	-
TB disease (after dose 1)	n/a	Any subject(s)	No dose 2 in same subject(s), keep in efficacy follow-up	-
Respiratory SOC AE (within 90 days after dose 1)	Grade ≥ 2	1 subject	No dose 2 in same subject(s), but keep in efficacy follow-up	-
Respiratory SOC AE (within 90 days after dose 1)	Grade ≥ 2 related	≥ 2 subjects	Clinical assessment & further investigation at investigator discretion	Ad hoc IDMC review
Respiratory SOC SAE	Related & Fatal	≥ 1 subject		
Respiratory SOC AE (within 90 days after dose 1)	Grade ≥ 3, related	≥ 2 subjects	No dose 2 in same subject(s) Clinical assessment & further investigation at investigator discretion	Study Hold, IMDC Review, VSMB

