6.6.9. Check contraindications to vaccination

Contraindications to vaccination must be checked at the beginning of each vaccination visit. Refer to Section 7.5 for more details.

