7.5. Contraindications to subsequent vaccination

The following events constitute absolute contraindications to further administration of M72/AS01_E. If any of these events occur during the study, the subject must not receive additional doses of vaccine but may continue other study procedures at the discretion of the investigator (see Section 9.4).

- Anaphylaxis following the administration of vaccine(s).
- Pregnancy (see Section 9.1.6).
- Any confirmed or suspected immunosuppressive or immunodeficient condition, including HIV-infection.
- Active TB disease.
- ***Grade 3 local symptoms redness and swelling, i.e. >100mm or Grade ≥2 respiratory AE following the administration of vaccine(s). (Amended: 29 January 2014).***

The following events constitute contraindications to administration of M72/AS01_E at that point in time; if any of these events occur at the time scheduled for vaccination, the subject may be vaccinated at a later date, within the time window specified in the protocol (see Section 6.5), or the subject may be withdrawn at the discretion of the investigator (see Section 9.4).

- Acute disease and/or fever at the time of vaccination.
 - Acute disease is defined as the presence of a moderate or severe illness with or without fever.
 - Fever is defined as temperature $\geq 37.5^{\circ}\text{C}/99.5^{\circ}\text{F}$ on oral, axillary or tympanic setting. The preferred route for recording temperature in this study will be axillary. **(Amended: 29 January 2014)**

Subjects with a minor illness (such as mild diarrhoea, mild upper respiratory infection) without fever can be administered all vaccines.

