The following local (injection site) and general AEs will be solicited:

Table 20 Solicited adverse events (Amended: 29 January 2014)

Solicited local (injection site) AEs	Solicited general AEs
Pain at injection site	Fatigue
Redness at injection site*	Fever
Swelling at injection site	Respiratory Symptoms†
	Headache
	Malaise
	Myalgia

*In case the principal investigator or designate is unable to determine the extent of redness on darkly pigmented skin, it will be reported as non-interpretable in the eCRF and Diary Card.

†Respiratory symptoms include **cough, blood in sputum, purulent sputum, shortness of breath or difficulties breathing, chestwall pain**

Note: Temperature will be recorded in the evening. Should additional temperature measurements be performed at other times of day, the highest temperature will be recorded in the eCRF.

9.1.4. Clinical laboratory parameters and other abnormal assessments qualifying as adverse events or serious adverse events

In absence of diagnosis, abnormal laboratory findings (e.g. clinical chemistry, haematology, urinalysis) or other abnormal assessments that are judged by the investigator to be clinically significant will be recorded as AE or SAE if they meet the definition of an AE or SAE (refer to Sections 9.1.1 and 9.1.2). Clinically significant abnormal laboratory findings or other abnormal assessments that are present at baseline and significantly worsen following the start of the study will also be reported as AEs or SAEs.

The investigator will exercise his or her medical and scientific judgement in deciding whether an abnormal laboratory finding or other abnormal assessment is clinically significant.

Toxicity grading scales for laboratory parameters [FDA, 2007] are presented in **Table 21**.

Table 21 Toxicity grading table for laboratory abnormalities (Amended: 29 January 2014)

	Mild (Grade 1)	Moderate (Grade 2)	Severe (Grade 3)	Potentially Life Threatening (Grade 4)*
Serum				
Sodium – Hyponatremia mEq/L	132 – 134	130 – 131	125 – 129	< 125
Sodium – Hypernatremia mEq/L	144 – 145	146 – 147	148 – 150	> 150
Potassium – Hyperkalemia mEq/L	5.1 – 5.2	5.3 – 5.4	5.5 – 5.6	> 5.6
Potassium – Hypokalemia mEq/L	3.5 – 3.6	3.3 – 3.4	3.1 – 3.2	< 3.1
Glucose – Hypoglycemia mg/dL	65 – 69	55 – 64	45 – 54	< 45
Glucose – Hyperglycemia	100 – 110	111 – 125	>125	Insulin requirements or hyperosmolar coma
Fasting – mg/dL	110 – 125	126 – 200	>200	
Random – mg/dL				

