9.2.3.2. Assessment of adverse events**9.2.3.2.1. Assessment of intensity**

The intensity of the following solicited AEs will be assessed as described:

Table 24 Intensity scales for solicited symptoms in adults (Amended: 29 January 2014)

Adults		
Adverse Event	Intensity grade	Parameter
Pain at injection site	0	None
	1	Mild: Any pain neither interfering with nor preventing normal every day activities.
	2	Moderate: Painful when limb is moved and interferes with every day activities.
	3	Severe: Significant pain at rest. Prevents normal every day activities.
Redness at injection site		Record greatest surface diameter in mm
Swelling at injection site		Record greatest surface diameter in mm
Fever*		Record temperature in °C/F
Headache	0	Normal
	1	Mild: Headache that is easily tolerated
	2	Moderate: Headache that interferes with normal activity
	3	Severe: Headache that prevents normal activity
Fatigue	0	Normal
	1	Mild: Fatigue that is easily tolerated
	2	Moderate: Fatigue that interferes with normal activity
	3	Severe: Fatigue that prevents normal activity
Respiratory symptoms (cough, blood in sputum, purulent sputum, shortness of breath or difficulties breathing, chestwall pain)	0	No symptoms
	1	Mild: symptoms that are easily tolerated
	2	Moderate: symptoms that interfere with normal activity
	3	Severe: symptoms that prevent normal activity
Malaise	0	Normal
	1	Malaise that is easily tolerated
	2	Malaise that interferes with normal activity
	3	Malaise that prevents normal activity
Myalgia	0	Normal
	1	Myalgia that is easily tolerated
	2	Myalgia that interferes with normal activity
	3	Myalgia that prevents normal activity

*Fever is defined as temperature $\geq 37.5^{\circ}\text{C} / 99.5^{\circ}\text{F}$ for oral, axillary or tympanic route, or $\geq 38.0^{\circ}\text{C} / 100.4^{\circ}\text{F}$ for rectal route. The preferred route for recording temperature in this study will be axillary.

The investigator will assess the maximum intensity that occurred over the duration of the event for all unsolicited AEs (including SAEs) recorded during the study. The assessment will be based on the investigator's clinical judgement.

The intensity should be assigned to one of the following categories:

1 (mild) = An AE which is easily tolerated by the subject, causing minimal discomfort and not interfering with everyday activities.

2 (moderate) = An AE which is sufficiently discomforting to interfere with normal everyday activities.

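### The rule barring dose 2 after a severe local reaction can be read as needing both redness and swelling in Protocol 6.4.5.4 and 7.5, but Table 6 implies either sign

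*Protocol*

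**What the plan says.** The rule appears three times in the current protocol text (Amendment 5).

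- **6.4.5.4, bullet:** "No second dose should be administered in a given subject who experiences Grade 3 redness and swelling, i.e". The threshold that follows is 100 mm or more.
- **Table 6, in the same section:** the event is "Redness/Swelling at injection site (within 30 days after dose 1"), at Grade 3 (above 100 mm), in any subject, and the action is no dose 2.
- **7.5, absolute contraindications:** Grade 3 local symptoms, given as "redness and swelling, i.e. >100mm or Grade ≥2 respiratory AE following the administration of vaccine(s").

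Protocol 6.6.9 makes 7.5 the operative list: "Contraindications to vaccination must be checked at the beginning of each vaccination visit", with 7.5 named for the details. Section 7.5 does not refer to Table 6.

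SAP 11.12 says that a subject with a large swelling reaction after dose 1 should not get dose 2. It calls this a per-protocol requirement and plans a list of subjects who got dose 2 regardless. It does not mention redness.

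**The concern.** A rule that decides whether an individual gets a second injection should have one meaning wherever a site meets it. In the bullet and in 7.5 the connector between the two signs is *and*. In 7.5 the same sentence then uses *or* before the respiratory criterion, which makes it easier to read the local criterion as needing both signs. Nothing in 7.5 says that one sign is enough.

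The pattern at stake is one sign above 100 mm without the other. It is plausible here because the footnote to Table 20 foresees that the investigator may be "unable to determine the extent of redness on darkly pigmented skin, it will be reported as non-interpretable". Under a both-signs reading, a swelling above 100 mm with redness that could not be assessed would not clearly meet 7.5, although Table 6 forbids the dose.

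**Working it through.** No arithmetic applies. The check is to set the texts side by side and ask what each implies for the same subject.

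**Connector and threshold**

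| Place | Connector | Threshold |
|---|---|---|
| Protocol 6.4.5.4, bullet | and | at least 100 mm |
| Protocol Table 6 | slash | above 100 mm |
| Protocol 7.5 | and | above 100 mm |
| Protocol 11.9 (grading) | each sign graded on one scale | Grade 3 above 100 mm |
| SAP 12.3.2 (grading) | each sign graded on one scale | Grade 3 above 100 mm; exactly 100 mm is Grade 2 |
| SAP 11.12 | swelling alone | large swelling reaction |

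**Consequence for dose 2**, taking the SAP's large swelling reaction to include the swelling of more than 100 mm described in Protocol 9.1.1:

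| Reaction after dose 1 | 7.5 read as both signs | Table 6 read as either sign | SAP 11.12 |
|---|---|---|---|
| Swelling and redness both above 100 mm | barred | barred | barred |
| Swelling above 100 mm, redness smaller or absent | not barred | barred | barred |
| Swelling above 100 mm, redness not interpretable | not clearly barred | barred | barred |
| Redness above 100 mm, swelling smaller or absent | not barred | barred | not addressed |

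**Which reading is intended?** Redness and swelling have separate rows in Table 24, each with the instruction "Record greatest surface diameter in mm". No combined grade is defined. With Table 6 and SAP 11.12, this points to either sign.

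**Threshold.** The bullet calls 100 mm or more Grade 3, while both grading scales put exactly 100 mm in Grade 2. The bullet errs on the protective side, and the difference matters only for a reading of exactly 100 mm.

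**What limits the risk?** Protocol 9.1.1 asks any subject who notices a large injection site reaction to contact the site and be seen, and has the event entered on its own eCRF screen. Table 7 schedules the recording of large swelling reactions for all subjects, including at Visit 4, when dose 2 is given. These steps bring the reaction to the investigator's attention but do not themselves bar the dose. The SAP 11.12 list can find an error only after the dose, and SAP 13.2 holds individual listings until the end-of-study analysis.

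**The case against.** The strongest reply is that *and* here is a list. Two symptoms share one threshold; 7.5 introduces them with a plural noun; and Protocol 11.9 joins the same two signs with *and* when it sets out their grading, where nobody would think that both must be present. The *or* in 7.5 only separates local from respiratory events. Table 6 sits directly under the bullet, and the SAP shows how the sponsor reads its own rule. For harm to follow, an investigator would have to take the narrower reading of 7.5, overlook Table 6, and inject after having evaluated a swelling above 100 mm.

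Most of this stands. It shows that the list reading is reasonable and the risk small. It does not remove the ambiguity from 7.5, which is the text consulted at the visit, and the SAP does not instruct sites.

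A second reply is that moving the bullet to above 100 mm gives up a slightly more protective limit. That is true at exactly 100 mm only, and the bullet's label of Grade 3 is wrong at that value under the protocol's own scale.

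Two stronger readings are tempting, and the documents support neither.

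- A reader might infer that the protocol contradicts itself in intent. Table 6, the separate grading and SAP 11.12 all point the same way, so this is an ambiguity of wording.
- A reader might infer that severe redness can be checked only in the safety and immune sub-cohort, because Table 24 asks for a diameter only for solicited events. But contraindications are checked in every subject at the dose-2 visit, and nothing prevents an investigator from measuring redness then.

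**Conclusion.** The concern holds as a minor inconsistency in a subject-level safety rule. Read conjunctively, 7.5 could permit a dose that Table 6 forbids. Either sign alone appears to be the intended trigger; that is an inference from Table 6, the separate grading of the two signs and SAP 11.12, since no passage states it outright.

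The number of subjects affected cannot be derived: the documents give no frequency for one sign above 100 mm without the other, and do not show how sites read the rule. The practical risk is limited by Table 6 and by the evaluation and recording of large swelling reactions in all subjects. The success criterion for efficacy, the alpha and the sample size do not depend on the wording.

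**What to change.** In the 6.4.5.4 bullet and in 7.5, write: Grade 3 redness and/or swelling (>100 mm) after dose 1. This matches Table 6 and settles the threshold in the bullet at the same time. Leave the respiratory criterion, Table 6 and the SAP as they are; the list planned in SAP 11.12 already follows the intended rule for swelling.

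The cost is one phrase in two places, by clarification letter or in an amendment, with no change to data collection or analysis. The wording dates from Amendment 5 (29 January 2014) and SAP section 9 puts the first subject's first visit in August 2014, so there was time to clarify it before any dose was given.
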